12.1.4 Test of Superiority for Lesion Count Variables Evaluator's Global Severity Score

This section provides the basic model and statistical approach which is used in combination with the multiple imputation procedures described in Section 12.1.9. Tests of superiority for the absolute change from Baseline in inflammatory and non-inflammatory lesions will be based on

based on an ANCOVA with factors of treatment and analysis center and the respective Baseline lesion count as a covariate If the treatment-by-analysis center interaction effect is significant at an alpha less than 0.10, then the effect will be included in the model; otherwise it will be removed.

12.1.5 Statistical Hypothesis Testing and Control of Multiplicity

In order to control the Type I error rate, testing of primary endpoints will be performed sequentially, in the order listed below:

IDP-126 Gel vs IDP-126 Vehicle Gel

- Superiority for Dichotomized EGSS
- Superiority for Absolute Change in Inflammatory Lesion Counts
- Superiority for Absolute Change in Non-Inflammatory Lesion Counts

Epiduo® Forte vs IDP-126 Vehicle Gel

- Superiority for Dichotomized EGSS
- Superiority for Absolute Change in Inflammatory Lesion Counts
- Superiority for Absolute Change in Non-Inflammatory Lesion Counts

IDP-126 Gel vs Epiduo® Forte

- Non-Inferiority for Dichotomized EGSS
- Non-Inferiority for Absolute Change in Inflammatory Lesion Counts
- Non-Inferiority for Absolute Change in Non-Inflammatory Lesion Counts
- Superiority for Dichotomized EGSS
- Superiority for Absolute Change in Inflammatory Lesion Counts
- Superiority for Absolute Change in Non-Inflammatory Lesion Counts

If all primary endpoint comparisons are statistically significant, then testing will continue for the secondary endpoints in the following order, for IDP-126 Gel vs IDP-126 Vehicle Gel:

- Percent change in inflammatory lesion counts from Baseline at Week 12
- Percent change in non-inflammatory lesion counts from Baseline at Week 12
- Percent of subjects who achieve at least a 2-grade reduction from Baseline and are "Clear" or "Almost Clear" at Week 8 in the EGSS
- Absolute change in inflammatory lesion counts from Baseline at Week 8
- Absolute change in non-inflammatory lesion counts from Baseline at Week 8
- Percent change in inflammatory lesion counts from Baseline at Week 8
- Percent change in non-inflammatory lesion counts from Baseline at Week 8

• Percent of subjects who achieve at least a 2-grade reduction from Baseline and are "Clear" or "Almost Clear" at Week 4 in the EGSS

- Absolute change in inflammatory lesion counts from Baseline at Week 4
- Absolute change in non-inflammatory lesion counts from Baseline at Week 4
- Percent change in inflammatory lesion counts from Baseline at Week 4
- Percent change in non-inflammatory lesion counts from Baseline at Week 4
- Percent of subjects who achieve at least a 2-grade reduction from Baseline and are "Clear" or "Almost Clear" at Week 2 in the EGSS
- Absolute change in inflammatory lesion counts from Baseline at Week 2
- Absolute change in non-inflammatory lesion counts from Baseline at Week 2
- Percent change in inflammatory lesion counts from Baseline at Week 2
- Percent change in non-inflammatory lesion counts from Baseline at Week 2
- Percent of subjects who achieve at least a 2-grade reduction from Baseline at Week 12 in the TSS
- Percent of subjects who achieve at least a 2-grade reduction from Baseline at Week 8 in the TSS
- Percent of subjects who achieve at least a 2-grade reduction from Baseline at Week 4 in the TSS
- Percent of subjects who achieve at least a 2-grade reduction from Baseline at Week 2 in the TSS

12.1.6 Descriptive Statistics

Descriptive statistics will be presented for the following parameters by treatment group for both the ITT and PP analysis sets:

- Frequency and percent distributions of the EGSS at Baseline and Weeks 2, 4, 8, and 12.
- Frequency and percent distributions of the dichotomized (two-grade reduction from Baseline and are Clear or Almost Clear; two-grade reduction from Baseline) EGSS at Weeks 2, 4, 8, and 12.
- Descriptive statistics including mean, median, standard deviation, minimum, and maximum will be used to summarize inflammatory and non-inflammatory lesion counts at Baseline and Weeks 2, 4, 8, and 12.
- Descriptive statistics including mean, median, standard deviation, minimum, and maximum will be used to summarize the absolute and percent change in inflammatory and non-inflammatory lesion counts at Weeks 2, 4, 8, and 12.

12.1.7 Missing Efficacy Data Imputations

Lesion Count Variable Missing Data Imputation

Missing data will be estimated by multiple imputation and subsequently analyzed. Missing lesion count data will be derived for the analysis using the method of Markov Chain Monte Carlo (MCMC) multiple imputation. The pattern of missing observations in each treatment group will not influence the missing value estimation in the other because the imputation is being conducted independently for each treatment group.

Multiple imputation and subsequent analysis will involve 4 distinct phases with these principal tasks:

1. Create a data set of subjects, one for each treatment group, with observed values and those needing estimation by MCMC. The missing lesion count values in each data set will be filled in using the MCMC method 5 times to generate 5 data sets. The resulting data sets for each treatment arm will be combined into one complete data set for each imputation.

Syntax:

```
proc mi data=datain out=dataout seed=&seed. nimpute=5 <options>;
  where trtpn=(1, 2, 3);
  mcmc chain=multiple;
  var baseline week2 week4 week8 week12;
run;
```

- 3. For each complete data set, the absolute change in lesion counts will be computed. Each complete data set will be analyzed as specified for the particular analysis.
- 4. The results from these analyses will be combined into a single inference using SAS PROC MIANALYZE.

A total of 6 random seeds will be needed to impute inflammatory lesion counts and non-inflammatory lesion counts for the five treatment groups. Those 6 random seeds have been prespecified by using a random number generator:

- Inflammatory Lesion Counts; IDP-126 Gel: Seed=1228911621
- Inflammatory Lesion Counts; Epiduo® Forte Gel: Seed=1083128177
- Inflammatory Lesion Counts; IDP-126 Vehicle Gel: Seed=138767001
- Non-Inflammatory Lesion Counts; IDP-126 Gel: Seed=239363547
- Non-Inflammatory Lesion Counts; Epiduo® Forte Gel: Seed=1663970906
- Non-Inflammatory Lesion Counts; IDP-126 Vehicle Gel: Seed=1896067066

EGSS Missing Data Imputation

A similar procedure will be used for the analyses based on proportion of EGSS successes wherein the ANCOVA analysis is replaced with a logistic regression analysis. Specifically, missing EGSS values from which the dichotomized EGSS is derived will be estimated by MCMC. The pattern of missing observations in each treatment group will not influence the

12.1.8 Subject Self-Assessments

Subjects will be asked to complete the Acne-Specific Quality of Life Questionnaire (Appendix 17.3). Descriptive statistics will be used to summarize the data reported for the questionnaire. No inferential analyses will be conducted.

12.2 Assessment of Safety

All safety assessments will be conducted using the safety analysis set.

Safety will be evaluated by tabulations of AEs, and Cutaneous Safety and Tolerability Evaluations. Cutaneous Safety Evaluation scores (erythema, scaling, hypo/hyper-pigmentation)

and Tolerability (itching, burning, and stinging) will be presented with descriptive statistics at Baseline and at Weeks 2, 4, 8, and 12 for each treatment group. In addition, the percent of subjects who experience a cutaneous reaction graded at a level of 3 at any point in the study following the first application of study drug will be tabulated. Frequencies and percentages for each outcome category will be included in these statistics. Mean values will be presented graphically by week and treatment group.

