3	Moderate	Non-inflammatory lesions predominate, with multiple inflammatory lesions evident: several to many comedones and papules/pustules, and there may or may not be 1 nodulocystic lesion
4	Severe	Inflammatory lesions are more apparent, many comedones and papules/pustules, there may or may not be up to 2 nodulocystic lesions

Safety Measurements:

Safety evaluations will include the following:

- The percent of subjects who experience a cutaneous reaction (erythema, scaling, hypo/hyper-pigmentation, itching, burning, or stinging) graded at a level of 3 at any point in the study following the first application of study drug.
- The percent of subjects who experience a cutaneous adverse event (AE) irrespective of severity grade at any point in the study following the first application of study drug.
- Changes from baseline in all safety laboratory values and vital sign measurements as summarized using descriptive statistics by treatment group and study visit.
- Subjects will be assessed for the occurrence of new and ongoing AEs.

Cutaneous safety and tolerability will be evaluated by tabulations of AEs and Cutaneous Safety and Tolerability Evaluation scores (scaling, erythema, hypo/hyper-pigmentation, itching, burning, and stinging) to be assessed at each study visit. Itching, burning and stinging (cutaneous tolerability) will be reviewed with the subject at each study visit as an average over the period since the previous visit. Scaling, erythema, and hypo/hyper-pigmentation (cutaneous safety) will be assessed by the evaluator at each visit. Cutaneous tolerability signs and symptoms that result in the subject requiring a concomitant therapy, interruption of treatment, or discontinuation from the study will be reported as an AE.

Statistical Methods

All statistical processing will be performed using SAS® version 9.4 or later unless otherwise stated.

Statistical significance for superiority analyses will be based on two-tailed tests of the null hypothesis resulting in p-values of 0.05 or less.

Non-inferiority of IDP-126 Gel to Epiduo® Forte will be assessed with 95% confidence intervals with the

following non-inferiority margins:

- 1) Absolute change from Baseline to Week 12 in inflammatory lesion counts: 2.1
- 2) Absolute change from Baseline to Week 12 in non-inflammatory lesion counts: 2.1

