8.2 Subject Exclusion Criteria

Subjects meeting any of the following criteria will be excluded from the study:

1. Use of an investigational drug or device within 30 days of enrollment or participation in a research study concurrent with this study.

- 2. Any dermatological conditions on the face that could interfere with clinical evaluations such as acne conglobata, acne fulminans, secondary acne, perioral dermatitis, clinically significant rosacea, gram-negative folliculitis, dermatitis, eczema.
- 3. Any underlying disease(s) or some other dermatological condition of the face that requires the use of interfering topical or systemic therapy or makes evaluations and lesion count inconclusive.
- 4. Subjects with a facial beard or mustache that could interfere with the study assessments.
- 5. Subjects with more than two (2) facial nodules.
- 6. Evidence or history of cosmetic-related acne.
- 7. Subject has a history of experiencing significant burning or stinging when applying any facial treatment (eg, makeup, soap, masks, washes, sunscreens, etc) to their face.
- 8. Female subjects who are pregnant, nursing mothers, planning a pregnancy during the course of the study, or become pregnant during the study.
- 9. Use of estrogens (eg, Depogen, Depo-Testadiol, Gynogen, Valergen, etc) for less than 12 weeks immediately preceding study entry; subjects treated with estrogens 12 or more consecutive weeks immediately prior to study entry need not be excluded unless the subject expects to change dose, drug or discontinue estrogen use during the study.
- 10. If female, subject has a history of hirsutism, polycystic ovarian disease or clinically significant menstrual irregularities.
- 11. History of regional enteritis, ulcerative colitis, inflammatory bowel disease, pseudomembranous colitis, chronic or recurrent diarrhea, or antibiotic-associated colitis.
- 12. Treatment of any type of cancer within the last 6 months, with the exception of complete surgical excision of skin cancer outside the treatment area.
- 13. Subject uses medications and/or vitamins during the study which are reported to exacerbate acne (azathioprine, haloperidol, Vitamin D, Vitamin B12, halogens such as iodides or bromides, lithium, systemic or topical mid-to super-high potency corticosteroids on the treatment area, phenytoin and phenobarbital). Multivitamins, including Vitamin A, at recommended daily doses, and Vitamin D at stable doses, are acceptable.

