11.1.2 Visit 2: Baseline Visit (Day 0)

If a washout is not needed, this visit may occur on the same day as the Screening Visit (Visit 1). If a washout is needed, Visit 2 (Baseline) must occur after the appropriate washout period based on the criteria provided in Section 8.2.

The following procedures will be conducted at this visit:

- 1. The baseline Acne-QoL questionnaire will be completed by the subject and collected prior to conducting any other study-related procedures.
- 2. Verify that the subject continues to meet the applicable inclusion/exclusion criteria as outlined in Sections 8.1 and 8.2.
- 3. Record any changes in medical history since screening.
- 4. Record changes in any concomitant medications or therapies since the previous visit under Prior and Concomitant Medications or Therapies. Check for prior and concomitant medications / therapies as per Section 9.4.
- 5. Perform a urine pregnancy test for all females who are premenses and FOCBP. The urine pregnancy tests will be supplied by the CRO/designee.
- 6. Perform an abbreviated physical examination, including measurements of weight and vital signs (blood pressure, heart rate, respiration rate, and oral temperature). Any abnormal physical examination findings will be recorded.
- 7. The evaluator will perform the Baseline efficacy evaluations including an assessment based on the EGSS, and counts of inflammatory and non-inflammatory lesions. The EGSS is performed prior to the lesion counting. Every effort should be made for the same qualified, validated evaluator to perform the efficacy evaluations at all visits from Baseline to Week 12 for the same subject.
- 8. If the subject presents with truncal acne and agrees to have their study drug applied to these areas, then TSS will be performed from Baseline to Week 12. Note: lesion counts will not be performed for truncal acne.
- 9. The evaluator will perform the Cutaneous Safety and Tolerability Evaluations. If the subject presents with truncal acne and agrees to have their study drug applied to these areas, then the Cutaneous Safety and Tolerability Evaluations will also be performed for these areas.
- 10. Collect blood samples for routine laboratory analysis (CBC/Diff, serum chemistry, and serum pregnancy for pre-menses females and FOCBP).
- 11. Select Sites Only Obtain representative photographs of the face.
- 12. Assign the subject the appropriate kit number (this number will be generated from the RTSM).

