- 13. Once a kit has been assigned to a subject, the kit should be pulled from pre-dispensing storage conditions, and kept in the secure drug storage area by an unblinded dispenser for approximately 10 to 15 minutes before dispensing to the subject.

14. The study coordinator or designee will weigh a pump from the assigned kit and dispense it to the subject. The pump will be weighed (with the cap on) using a calibrated scale. Record the weight of the pump to the nearest 0.1 g. A study diary calendar will also be dispensed and the subject will be instructed to bring it to all subsequent visits.

- 15. The study coordinator or designee will instruct the subject on the proper application procedure for the study drug per Section 10.1.3, and will provide written subject use instructions to the subject (Appendix 17.1). For the first application, the subject will apply the study drug at the study center under the direction of the study coordinator or designee. The study drug should be applied after all clinical assessments. The study coordinator or designee will instruct the subjects to apply the study drug once daily at home at the same time of day, and will instruct the subject to use an investigator-approved, non-medicated sunscreen of at least SPF 15, and to wear protective clothing during the day (eg, a hat) if exposure cannot be avoided.
- 16. Record any AEs or changes in AEs since the screening visit and/or reported spontaneously by the subject.
- 17. Schedule the next study visit at Week 2 (Day 14 ± 3 days). Remind the subject not to apply study drug on day of next study visit.

NOTE: At the Baseline and Week 12 visits, serum pregnancy testing is **mandatory** for all pre-menses females and females of childbearing potential.

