11.3.1 Cutaneous Safety Evaluations

Cutaneous safety will be evaluated through an assessment, conducted at the time of the study visit, of selected local signs (i.e., signs present at the study drug application site) that include the following: scaling, erythema, hypopigmentation, and hyperpigmentation. The evaluator will assess all cutaneous safety signs. For subjects treating (optional) truncal acne, cutaneous safety evaluations will also be conducted on this area throughout the course of the treatment/study, and recorded separately.

Cutaneous safety signs that result in the subject's requiring a concomitant therapy, interruption of treatment, or discontinuation from the study, will be reported as an AE.

Scaling:

0 – None No scaling

1 – Mild Barely perceptible, fine scales present on limited areas of the face

2 – Moderate Fine scale generalized to all areas of the face

3 – Severe Scaling and peeling of skin over all areas of the face

Ervthema:

0 – None No evidence of erythema present

1 – Mild Slight pink coloration

2 – Moderate Definite redness

3 – Severe Marked erythema, bright red to dusky dark red in color

Hypopigmentation:

0 – None No evidence

1 – Mild Slight, barely perceptible

2 – Moderate Definite, evident 3 – Severe Marked, prominent

Hyperpigmentation:

0 – None No evidence

1 – Mild Slight, barely perceptible

2 – Moderate Definite, evident3 – Severe Marked, prominent

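### The grade 3 cutaneous reaction percentage ignores the pre-dose Baseline score, so a severe sign that persists from Baseline is counted like a new one

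*Combined protocol and SAP*

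**What the plan says.** The synopsis (Safety Measurements) and Section 12.2 set the same measure. The synopsis lists the items as a "cutaneous reaction (erythema, scaling, hypo/hyper-pigmentation, itching, burning, or stinging" event, and counts a subject if one is "graded at a level of 3 at any point in the study following the first application of study drug". Section 12.2 repeats this as a "cutaneous reaction graded at a level of 3 at any point in the study following the first application of study drug" and says only that the percentage will be tabulated. Neither place requires the score to be new or worse than Baseline.

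A pre-dose score exists. Under Section 11.1.2, "The evaluator will perform the Cutaneous Safety and Tolerability Evaluations" at the Baseline visit. Later in the same list, "For the first application, the subject will apply the study drug at the study center", after all clinical assessments are done.

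The scales record status, not change. Section 11.3.1 states: "Cutaneous safety will be evaluated through an assessment, conducted at the time of the study visit, of selected local signs". Grade 3 erythema, for example, is "Marked erythema, bright red to dusky dark red in color".

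The remaining cutaneous analysis is descriptive: category frequencies at Baseline and Weeks 2, 4, 8 and 12 by arm, with mean plots.

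**The concern.** Subjects enter with an EGSS of 3 or 4 and 30 to 100 inflammatory lesions (Section 8.1). Section 11.2.2 defines papules, pustules and nodules as erythematous, and the EGSS table in Section 11.2.1 notes that resolving papules may be hyperpigmented. The disease itself can therefore produce some of the signs that the measure counts. On a static scale an unchanged grade 3 scores 3 again at Week 2, and a single persisting item at a single visit is enough to count the subject.

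At stake is what the percentage means. A reader will take a rate of severe cutaneous reactions after first application as a rate of events that arose on treatment. If it also contains signs that were already there, it is too high in each arm, vehicle included, and a reader who forms a ratio from the table gets one that is too close to 1.

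**Working it through.** The plan gives no expected rate, Baseline rate or power for this measure, so there is no figure to reproduce. The check is a comparison of sections, followed by an illustration on assumed rates.

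**1. Can the planned outputs separate new from persisting grade 3?**

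| Data | Link to Baseline in the plan |
|---|---|
| Adverse events (12.2.1) | Treatment-emergent by onset date |
| Laboratory values (12.2.2) | Change from Baseline and shift tables |
| Vital signs (12.2.3) | Change from Baseline and shift tables |
| Cutaneous scores (12.2) | By-visit frequencies including Baseline; no change or shift within a subject |

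The by-visit frequencies show each arm's Baseline burden. They cannot show whether a subject at grade 3 in Week 4 was also at grade 3 at Baseline.

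**2. Does eligibility rule out a Baseline grade 3?** Section 8.2 sets no upper limit on the Baseline erythema, scaling or pigmentation score. Exclusion 7 concerns history, and only two symptoms: "Subject has a history of experiencing significant burning or stinging when applying any facial treatment". Other exclusions narrow the scope (see the objection) but do not cap the score.

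**3. Size if carry-over occurs.** Let

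- c = (share at grade 3 at Baseline) × (share of those still at grade 3 at a post-dose visit);
- e = true rate of new grade 3, taken as independent of carry-over.

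Then the tabulated rate is c + (1 − c)e, and the difference between two arms is (1 − c)(e₂ − e₁). Every value of c and e below is assumed.

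*New rates of 2% and 6% (true ratio 3.0, difference 4.0 points):*

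| c | Lower arm | Higher arm | Difference | Ratio | Carried over per 220 |
|---|---|---|---|---|---|
| 0% | 2.00% | 6.00% | 4.00 | 3.0 | 0 |
| 1% | 1 + 0.99×2 = 2.98% | 1 + 0.99×6 = 6.94% | 3.96 | 2.3 | 2.2 |
| 3% | 3 + 0.97×2 = 4.94% | 3 + 0.97×6 = 8.82% | 3.88 | 1.8 | 6.6 |
| 5% | 5 + 0.95×2 = 6.90% | 5 + 0.95×6 = 10.70% | 3.80 | 1.6 | 11 |

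*New rates of 2% (active) and 0.5% (vehicle) (true ratio 4.0, difference 1.5 points):*

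| c | Active | Vehicle | Difference | Ratio |
|---|---|---|---|---|
| 0.5% (1% at Baseline, half persisting) | 2.49% | 1.00% | 1.49 | 2.5 |
| 2% (all persisting) | 3.96% | 2.49% | 1.47 | 1.6 |
| 5% (all persisting) | 6.90% | 5.47% | 1.43 | 1.3 |

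The arm size of 220 is from Section 12.8.2, with the two vehicle arms combined. In both sets the difference shrinks only by the factor 1 − c, while the level and the ratio can change a good deal. With c = 0 the two definitions agree.

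**The case against.** Several counter-arguments have force.

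- **A difference between arms is not hidden.** A reader might infer that the measure conceals a tolerability difference between IDP-126 Gel and Epiduo Forte Gel. The documents do not support that. Randomization makes carry-over similar across arms on average, the absolute difference is nearly preserved, and no ratio, test or decision rule is planned for this tabulation. This objection stands.
- **Inflation is conditional.** A reader might also infer that every arm's rate is certainly overstated. That needs subjects who are at grade 3 at Baseline and still at grade 3 after dosing. A Baseline grade 3 that resolves by Week 2 and does not return is never counted. The exclusions for rosacea, dermatitis, eczema and irritating products, the washouts of facial retinoids, peels and corticosteroids, and the extreme grade 3 definitions for scaling and the three symptoms all make this less likely. They say less about erythema and pigmentation. This stands as a limit on size.
- **The text does not attribute the sign to study drug.** It speaks of a reaction after the first application, which could be meant as new onset. No rule says so, and that ambiguity is a reason to define the term.
- **Other routes exist.** Signs or symptoms that need concomitant therapy, interruption or discontinuation are reported as adverse events, which have an onset rule, and the synopsis counts cutaneous adverse events of any severity separately. These do not classify the grade 3 scores themselves.
- **A simple rule of being above Baseline can undercount.** A subject at grade 3 at Baseline who clears and then returns to grade 3 on treatment would never be counted. This is right, and the fix must deal with it.
- **A separate SAP may define the measure.** Section 12 says that one will describe all analyses. No such definition appears in the text available for this review. If the SAP has one, the protocol wording should match it.

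**Conclusion.** The point holds as a matter of definition. The tabulated percentage does not use the pre-dose score, and no planned summary separates new from persisting grade 3 within a subject. Whether this matters numerically depends on a Baseline grade 3 rate and a persistence rate that the documents do not give. Over the assumed 1% to 5% carried over, with new rates of 2% and 6%, the reported level rises by about 1 to 5 points in each arm and the ratio falls from 3.0 to between 2.3 and 1.6. The difference stays between 3.8 and 4.0 points. The consequence is an overstated level and a diluted ratio in a descriptive safety table. It is neither a bias toward one arm nor a threat to the efficacy conclusions. This is an inexpensive improvement, not a serious flaw.

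**What to change.** In the synopsis (Safety Measurements) and Section 12.2, tabulate treatment-emergent grade 3. Define it as either of the following, for the same sign or symptom and the same application area (face or trunk, which Sections 11.3.1 and 11.3.2 already record separately):

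1. a post-baseline grade 3 that is higher than the subject's Baseline grade; or
2. a return to grade 3 after a lower post-baseline grade.

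Keep the present any-grade-3 count beside it, so that nothing already specified is lost. Add a shift table of Baseline against worst post-baseline grade, by item and arm. Settle the definition before unblinding, so that it is not a post hoc choice.

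The cost is a clause in two places, one extra row and one extra table. The scores are already collected, and no endpoint or sample size changes. One limitation remains: a subject at grade 3 at Baseline who never improves is at the top of the scale and cannot register worsening on that item. The retained any-grade-3 count and the shift table will show such subjects.
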